### ***Secondary objectives***

The secondary objectives are:

1. To determine if there is more improvement in improvement regulatory emotional self-efficacy, treatment readiness, and aggression in the experimental than control group during, directly after completing, and three months after completing the internet-based intervention 'Aggression'.
2. To determine if there is more improvement on dynamic risk in the experimental than the control group after completing the internet-based intervention 'Aggression'.
3. To determine if the number of face-to-face treatment contacts over a period of 37 weeks is lower in the experimental than the control group.
4. To determine if the level of engagement with the intervention measured at the beginning, halfway and at the end of the internet-based intervention Aggression, and the adherence to the intervention, is a predictor for effectiveness.
5. To map experiences with the internet-based intervention Aggression of forensic psychiatric patients that followed (part of) the intervention.
6. To map experiences with the internet-based intervention Aggression of therapists that used the intervention in at least five patients.

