#### 4.4 Sample size calculation

This sample size calculation is conservatively based on the ability to detect at least a moderate effect of Cohen's  $d = .50$  on the primary outcomes at follow-up (T3). A power analysis was conducted with G\*power. The analysis was conducted with a moderate effect size of 0.5, a  $\beta$ -power of .8, a p-value of 5%, and an independent two-sided t-test as method of analysis. This analysis showed that 64 patients need to be included in each condition. This means that a total of 128 patients needs to be included. Accounting for a drop-out of 20%, the goal for inclusion is set at a total of 154 patients. It is important to note that participants in the experimental condition are considered as a 'drop-out' when they don't fill out the questionnaires at all measuring moments, not when they stop using the intervention. In other words: patients can stop using the intervention. In other words: patients can stop using the intervention, but can still complete their participation in the study if they fill out all questionnaires. Adherence to the intervention is not the same as drop-out from the study, since it is a different concept. The main reason for this is that earlier research has shown that patients often stop using these interventions before all lessons are completed, so it is not realistic to expect that all patients fully complete the intervention. In order to account for this, the number of completed lessons will be included as a moderator for effectiveness in the analyses to investigate whether adherence is related to effectiveness. Additionally, a sub-goal of this study is to determine whether engagement is a predictor of adherence and effectiveness to incorporate non-adherence to the intervention in the study. The intended 154 patients will be included at four different organizations that all have multiple forensic outpatient clinics.

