studies with this target group has shown that this can be an additional motivator for patients to participate. In all communication, these rewards will be mentioned to ensure that the patients are aware of the fact that they will be compensated for their invested time. To prevent that patients drop out during data collection, they will receive one voucher halfway, and one after completing all questionnaires. Additionally, when patients don't fill out questionnaires at one of the measurement moments, they will be reminded via e-mail and if that is not effective, the researcher will contact the therapist, who will remind the patient of the questionnaires. Sixth, in line with this, to prevent drop-out due to high time investment, the four selected questionnaires are kept as short as possible and filling them out will only take a couple of minutes. Also, data from risk assessment instruments that are already being administered is used to prevent additional time investment from patients and therapists. Seventh, as is the case with any internet-based intervention, patients might not be fully adherent, meaning that they do not complete the entire intervention. While this is a realistic risk, this does not threaten the feasibility of this study, because this is also an interesting and relevant result. If, even if therapists and patients receive much support in using the intervention, patients still do not complete the intervention, this has implications for its application in clinical practice. Additionally, adherence to the intervention will be used as a predictor for effectiveness to investigate if there is a dose-response relationship. It is important to emphasize that patients that do not fully complete the intervention, but still fill out all questionnaires, are not considered as a drop-out. Finally, it can be challenging to gather large sample sizes in forensic mental healthcare. To overcome this, data collection will take place in four organizations, that all have multiple outpatient clinics where patients can be included. The feasibility of including approximately 38 patients per organization – which all have multiple outpatient clinics - is elaborately discussed with representatives from the organizations that also participate in the project team that coordinates this study. Furthermore, initial contact with therapists has underlined the expectation that the intended number of participants can be reached.

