Participating therapists are informed of the group the patient is allocated to and will explain this to the patient. If a patient is randomized into the control condition, the therapist is instructed to provide treatment as usual, and can be contacted by the researcher in case a patient did not fill out questionnaires at T0, T1, T2 or T3. If a patient is randomized into the experimental group, the therapist is asked to start with the intervention 'Aggression'. Specifically, the therapist will shortly explain the goal, content and nature of the internet-based intervention and explain to the patient that they will receive one lesson per week for the next 10 weeks. Additionally, the therapist will provide written feedback on the assignments of the patients. All participating therapists are trained in the use of these types of interventions and thus know how to provide feedback. To increase the feasibility of this study and reach the intended number of participants, therapists will receive additional support from researchers to remind them to introduce the intervention. The main reason for this is that implementation research on these types of internet-based interventions in Dutch forensic outpatient care has shown that, even though therapists have the intention to use the intervention, they often forget to introduce the intervention. Additionally, if they introduced the intervention, therapists often do not mention it in their treatment sessions. Consequently, participating therapists will be regularly reminded to introduce and keep on discussing the internet-based interventions with the patients in the experimental condition.

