### ***Step 3: Inclusion and informed consent – Week 8-11***

If the patient agrees to be contacted by the researcher, the researcher will contact them via their preferred way of communication, as indicated on the initial consent form. The patient is asked to participate by the researchers and not by the therapist to prevent that the patient feels obliged to participate if their therapist asks them – which is especially relevant for patients who follow treatment as part of a sentence. The patient will receive information about the goal and relevance of the study, the required effort, the rewards for participating, the consequences of randomization, and the nature of the internet-based intervention. The letter that contains all this information might be difficult to understand, so a short summary in simple language is added to make sure all patients are able to understand the goal and means of this study. Also a short video will be made to ensure that all the information is received and understood. The researcher will clearly communicate that during the data collection period, patients in the control group will not be able to use any of internet-based interventions offered by Minddistrict. However, once the study is finished, the patient can use the intervention. Consequently, if a patient is extremely motivated to use an internet-based intervention, they can decide not to participate in the study. The patient also will be given multiple opportunities to ask questions and to think five days about whether to participate. If it is possible for the researcher to visit the patient in real life at the treatment location, informed consent will be provided in person, after a waiting period of at least five days. If this is not possible, the informed consent form will be sent to the patient via post, after which a signed form can be returned by the patient via an included, stamped envelope. However, due to the psychosocial problems of this target group, it might not be possible or desirable for all patients to receive the informed consent form via post, for example because they don't have a fixed living address at that point in time, or because they don't want their housemates to know about participation in the study and/or in forensic care in general. If this is the case, and if both other options are not feasible, the informed consent will be e-mailed to the patient, after which they have time to read it. After five days, verbal informed consent will be obtained via a recorded videoconferencing session. In this way, the process of informed consent is adapted to the characteristics of the patient.

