#### ***Research objective 1: Self-efficacy, treatment readiness, and aggression***

To identify whether there are changes in dependent variables between the experimental and control group on baseline (T0), during the intervention (T1), post-intervention (T2) and follow-up assessment (T3), multilevel repeated-measures linear mixed models will be used. This analysis method accounts for autocorrelation within participants and missing data. Time and group will be used as fixed factors, along with their interactions, and participants are modelled as random factor. Interaction effects will be studied to identify whether the changes over time differed between groups. Main effects for time will be used to investigate whether the scores of all participants changed over time. In order to provide more insight into the main findings, Least-significant difference (LSD) post-hoc independent t-tests with Bonferroni correction will be performed to test for significant between-group differences and changes over time per group.

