The control group of this study will not receive the Aggression intervention, or any other type of internet-based intervention, during the data collection period. After that, these interventions can be used, which will be clearly communicated. Not following these interventions is not expected to have a negative impact on the quality of treatment of the participants in the control condition. First of all, at this point in time, it is not yet clear whether internet-based interventions Aggression actually result in better treatment outcomes in Dutch forensic mental healthcare. This means that participants in the control condition are not denied evidence-based care, simply because these interventions are not evidence-based yet. Furthermore, research with log data and interviews has shown that at this point, many patients do not have access to internet-based interventions at all, mostly because their therapist does not introduce these modules. To specify: one study showed that only 54% of all therapists working at an organization used the modules, of which the largest part used it with very few patients [21]. This implies that the use of internet-based interventions is not a part of standard care yet, meaning that participants in the control condition are not denied standard care procedures.

To summarize: in order to be able to deliver high-quality, evidence-based care, it is essential to investigate whether internet-based interventions that have been used for several years are indeed effective.

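### Completed lessons cannot moderate the between-arm effect, because every control has zero lessons; the slope that can be estimated within the experimental arm is an unadjusted observational association, and section 10 does not specify it

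*Combined protocol and SAP*

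**What the plan says.** Three places in the protocol promise an analysis of adherence against effectiveness.

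- Section 4.4, as part of its allowance for incomplete use of the module: "the number of completed lessons will be included as a moderator for effectiveness in the analyses to investigate whether adherence is related to effectiveness".
- Section 4.5: "adherence to the intervention will be used as a predictor for effectiveness to investigate if there is a dose-response relationship".
- Section 2, secondary objective 4, asks whether engagement "and the adherence to the intervention, is a predictor for effectiveness".

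The control arm has no lessons by design. Section 8.3 (Step 3) says that during data collection "patients in the control group will not be able to use any of internet-based interventions offered by Minddistrict", and section 11.4.2 says: "The control group of this study will not receive the Aggression intervention, or any other type of internet-based intervention, during the data collection period". Under section 8.2 the therapist starts the module only once the patient has been allocated to the experimental group.

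Section 10 does not contain the promised analysis. The mixed model in section 10.1 is described as follows: "Time and group will be used as fixed factors, along with their interactions, and participants are modelled as random factor". It has no lessons term. Section 10.2 (objective 4) regresses change scores on engagement, and finished lessons appear there only as an outcome to be predicted from engagement. The regressions are simple linear ones with no covariates named.

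**The concern.** A moderator of a randomised effect has to take values in both arms and should be fixed before treatment starts. Completed lessons meets neither condition. If the word is taken at face value, the model has a term that the data cannot inform.

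If the analysis is read instead as a slope within the experimental arm, it compares patients who went on with the module with patients who stopped. Those groups were not formed by randomisation. The protocol itself names factors that could drive both lessons and outcome:

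- Section 8.1.1 describes treatment readiness as bearing both on engagement with treatment and on therapeutic change.
- Section 3.3 says that missed sessions and psychosocial crises delay the lessons.
- Section 1 attributes non-adherence largely to therapists not introducing or discussing the module, and allows that patient characteristics may also explain it.

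At stake is how a null or weak randomised result would be read. If patients who completed more lessons improved more, the report could describe this as dose-response even though the module did nothing. Because section 10 is silent, the analyst would also have to choose the model after seeing the data.

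**Working it through.** The documents state no figure for this analysis, so there is none to reproduce. The only number taken from the plan is 64 patients per condition (section 4.4), used below as the size of the experimental arm.

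**Step 1. Can lessons moderate the between-arm effect?** Let G = 1 for experimental and 0 for control, and let L = completed lessons (0 to 10). For controls, G = 0 and L = 0, so G × L = 0 = L. For experimental patients, G = 1, so G × L = L. The columns L and G × L are therefore identical for every patient. Checked numerically with 64 per arm:

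- Columns 1, G, L, G × L: rank 3 of 4.
- Four-visit form, each of these crossed with time: rank 12 of 16.
- Columns 1, G, L only: rank 3 of 3. This model can be fitted, but the slope on L comes only from the experimental arm.

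This step is algebra and needs no assumption beyond zero lessons in controls.

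**Step 2. How far could the within-arm slope mislead?** Assume that the module has no effect, and that an unmeasured trait is correlated r with both lessons and outcome. The value of r is an assumption, shown over a range. The induced correlation between lessons and outcome is r × r. By the Fisher z approximation with n = 64:

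- z = atanh(r²) × √(64 − 3) = atanh(r²) × 7.81
- P(two-sided p < 0.05) = P(Z > 1.96 − z) + P(Z < −1.96 − z)

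For r = 0.4: r² = 0.16, atanh = 0.1614, z = 1.26, probability 24.3%.

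A simulation (20,000 runs; 64 per arm; lessons rounded and limited to 0–10, with mean about 5 and SD about 3, also assumptions) gives nearly the same rates:

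| r | r² | Fisher z | Simulated | Spurious difference over 10 lessons |
|---|---|---|---|---|
| 0 | 0 | 5.0% | 4.8% | 0.00 SD |
| 0.2 | 0.04 | 6.1% | 5.9% | 0.15 SD |
| 0.3 | 0.09 | 10.9% | 10.9% | 0.33 SD |
| 0.4 | 0.16 | 24.3% | 24.0% | 0.57 SD |
| 0.5 | 0.25 | 51.4% | 50.4% | 0.89 SD |

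The rates are per outcome, and there are three outcomes.

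**Step 3. Is the randomised comparison affected?** In the same simulation the between-arm test rejected in 5.0% to 5.1% of runs at every r, so it is not.

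**Step 4. What would an instrumental-variable estimate add?** With no lessons in controls and no covariates, the estimate is (mean outcome, experimental − mean outcome, control) ÷ mean lessons in the experimental arm. That is the intention-to-treat effect divided by a constant. In the simulation it averaged about zero at every r, so it avoids this confounding. But it only rescales the randomised result and does not show whether patients who did more lessons benefited more.

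**The case against.** The strongest reply is that the plan never writes a group × lessons term. Section 4.4 explains its own use of the word as asking whether adherence is related to effectiveness, and section 4.5 and objective 4 both say predictor. On that reading the intended analysis is a within-arm slope loosely called a moderator, and it can be fitted. This stands. A reader might infer from the rank result that the planned analysis must fail. The documents do not support that: they rule out moderation of the between-arm effect, but not a slope within the experimental arm.

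A second reply is that confounding by motivation is not demonstrated. This also stands. Section 1 gives therapist behaviour as an important reason for non-adherence and mentions patient characteristics only as a possible further one. No document supplies a correlation, and at r = 0.2 the inflation is slight.

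A third reply is that nothing decisive depends on this analysis. A reader might infer that the trial's verdict on effectiveness could be driven by adherence. It could not: the rules in sections 8.1 and 10.1 use between-arm comparisons only, section 10.1 specifies intention to treat, and section 4.5 speaks of investigating whether a dose-response exists, not of asserting one. Nor is this the plan's only response to low adherence. It also has therapist reminders, engagement as a predictor, interviews open to patients who stopped early, and a comparison with real-world log data.

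None of these replies supplies the missing specification, a baseline adjustment or a causal caveat.

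**Conclusion.** The point holds in this form. Moderation of the between-arm effect by completed lessons is not estimable, given that controls have no access. The version that is estimable is an observational slope in the experimental arm. Section 10 does not specify it, and nothing guards it against common causes that the protocol itself describes. The possible size runs from negligible (about 6% false-positive slopes per outcome at r = 0.2) to serious (about 50% at r = 0.5), with 64 experimental patients and no module effect. Where the trial would fall in that range is unknown, because r is assumed and the documents show only that confounding is plausible. The primary intention-to-treat comparison and the effectiveness rules are untouched. This is a defect of a secondary analysis and of how its result could be reported.

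**What to change.** 1. In section 4.4, delete the moderator role for completed lessons.
2. In section 10.2, specify an exploratory regression within the experimental arm of the T3 score (and, separately, the T2 score) on completed lessons. Adjust for the T0 score of that outcome and for T0 CVTRQ, entering CVTRQ once only when it is the outcome. Both are already collected (Table 1).
3. State that the slope is an association, and is not to be reported as dose-response or as evidence of effectiveness. Say that adjustment removes confounding only in part, since therapist behaviour and crises are not covered by the T0 scores.
4. Reconcile objective 4, sections 4.4 and 4.5, and section 10.2, so that all describe the same analysis.

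Optionally, add an exploratory instrumental-variable per-lesson estimate with allocation as the instrument. It should be stated that it rescales the intention-to-treat effect, will have a wide confidence interval, and assumes that allocation acts only through lessons. That assumption is doubtful here: allocation is open, and section 8.2 has therapists of experimental patients reminded to keep discussing the module. The estimate does not answer objective 4.

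The cost is some added wording, slightly more analysis work and a weaker adherence claim. No extra patients or measurements are needed.

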#### 4.5 Feasibility of the study

As is the case with any RCT in clinical practice, a potential barrier is the inclusion of enough participants. Especially in forensic mental healthcare, this can be problematic. However, there are multiple reasons and measures that are taken to increase the chance of successful completion of this RCT.

First of all, the intervention that is investigated in the RCT is already introduced in practice, and thus is not new. Consequently, therapists do not require training, already have experience in using similar interventions, and ‘teething problems’ that often occur when introducing new interventions in practice will not occur because these interventions have been used for over ten years.

Second, implementation research has shown that – while a large share of therapists don’t actively use these interventions, there are several therapists that do use these interventions relatively often and thus are quite experienced. In this study, therapists that have experience with and thus are able to successfully use these internet-based interventions will be included. Additionally, qualitative research into needs and wishes from clinical practice regarding technology in forensic mental healthcare has shown a high need for evaluation research of these internet-based interventions. [17, 19]. This finding, combined with experiences from clinical practice, shows that therapists see the urgency and relevance of this study, which is expected to positively contribute to their intrinsic motivation to participate in this study. Third, a common problem with these types of interventions is that they are not used as often as might be expected by most therapists, even though they express the intention to do so and are able to identify multiple potential benefits [21]. The main reason for this ‘intention-behaviour gap’ is that therapists often forget to introduce these modules to patients, and if they are introduced, they often don’t remember to discuss them during treatment sessions. This problem can be addressed by regularly reminding therapists to introduce and keep on using the intervention [24]. Consequently, during data collection, researchers and the secretary of the clinic will send regular reminders to participating therapists via e-mail and phone. Also, the study and accompanying intervention will be integrated as a fixed topic in intakes and multidisciplinary meetings [multidisciplinair overleg, MDO]. Fourth, while this is not as common, it might be that patients do not see the added value of the internet-based intervention. This will be accounted for by providing patients with a flyer and short information video on the content of the intervention. The content of these information materials will be tailored to the reading skills and preferences of patients. Fifth, another barrier might be that patients are not motivated to participate in data collection. To account for this, patients in the experimental and control condition receive a financial compensation. Experience with other

studies with this target group has shown that this can be an additional motivator for patients to participate. In all communication, these rewards will be mentioned to ensure that the patients are aware of the fact that they will be compensated for their invested time. To prevent that patients drop out during data collection, they will receive one voucher halfway, and one after completing all questionnaires. Additionally, when patients don't fill out questionnaires at one of the measurement moments, they will be reminded via e-mail and if that is not effective, the researcher will contact the therapist, who will remind the patient of the questionnaires. Sixth, in line with this, to prevent drop-out due to high time investment, the four selected questionnaires are kept as short as possible and filling them out will only take a couple of minutes. Also, data from risk assessment instruments that are already being administered is used to prevent additional time investment from patients and therapists. Seventh, as is the case with any internet-based intervention, patients might not be fully adherent, meaning that they do not complete the entire intervention. While this is a realistic risk, this does not threaten the feasibility of this study, because this is also an interesting and relevant result. If, even if therapists and patients receive much support in using the intervention, patients still do not complete the intervention, this has implications for its application in clinical practice. Additionally, adherence to the intervention will be used as a predictor for effectiveness to investigate if there is a dose-response relationship. It is important to emphasize that patients that do not fully complete the intervention, but still fill out all questionnaires, are not considered as a drop-out. Finally, it can be challenging to gather large sample sizes in forensic mental healthcare. To overcome this, data collection will take place in four organizations, that all have multiple outpatient clinics where patients can be included. The feasibility of including approximately 38 patients per organization – which all have multiple outpatient clinics - is elaborately discussed with representatives from the organizations that also participate in the project team that coordinates this study. Furthermore, initial contact with therapists has underlined the expectation that the intended number of participants can be reached.

To conclude: while any RCT on internet-based interventions in clinical practice is challenging, the set-up of this project is based on findings of and recommendations arising from research on implementation of these interventions in forensic mental healthcare. Additionally, several researchers with ample experience with RCTs on internet-based interventions and research in forensic mental healthcare are involved in this project, and the study design is based on their experiences and lessons learned from earlier projects. It is expected that, especially due to the fact that these interventions are not new for therapists and that they will receive ample support from the researchers, the intended number of participants will be reached.

